## 4 STUDY EVALUATIONS AND MEASUREMENTS

### 4.1 Efficacy Evaluation

#### 4.1.1 Primary Outcome

**Opioid dose**, as measured by prescribed milligrams of daily MED, is the primary study outcome. The primary outcome will be examined at baseline and months 6, 12, and 18 using opioid prescription data (**Table 3**). Prescribing data (including drug name, start and stop dates, dose, and frequency) will be derived from the EHR and provided by the PCORnet STAR CRN warehouse common data model (CDM). The field generally accepts prescribing data as documenting ingestion; other current and previously published studies also use prescribed dose as the primary endpoint. However, we recognize that ingestion may not be the same as the prescribed regimen. We will analyze the absolute (primary) decrease (or increase) in opioid MED from the baseline period (average of 90 days prior to randomization) until 18 months after randomization. We also will examine percentage decrease. Total morphine equivalents for each prescription will be calculated by multiplying the quantity of each prescription by the strength of the prescription (milligrams of opioid per unit dispensed). The quantity-strength product is then multiplied by conversion factors derived from published sources to estimate the milligrams of morphine equivalent to the opioids dispensed in the prescription. The total average dose in morphine equivalents per day supplied is calculated by summing the morphine equivalents for each prescription filled during a given period and dividing by the number of days supplied.

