#### *Missing Data*

The study will implement multiple procedures to prevent and reduce the amount of missing data and use appropriate statistical procedures to evaluate whether the results are robust to missing data. The risk of missing patient-reported outcome measures has been reduced by limiting the number of visits and assessments to those essential to achieve study goals and using “short” versions of instruments to

reduce burden. It is possible, however, that there may be some nonresponse to the 6- and 12-month patient reported outcome surveys. The sample size calculation assumed as high as 25% non-response at 12 months. EHR-derived data on opioid dosage is expected to be virtually complete based on standard PCORnet data extraction procedures, yet sample size calculations allow for up to 12% missing data at 12 months from lost to follow-up within the EHR or withdrawal of consent for use of EHR data. To reduce the risk of being unable to calculate the primary outcome because of missing or uninterpretable dosing instructions, MED will be derived using only the standardized and highly accurate fields: drug name, strength, and number of pills. In the event of missing medication information for a prescription (such as strength or number of pills), we will impute medication information from the 2 closest prescriptions by date, using an algorithm developed by our clinical content experts, and conduct sensitivity analyses with and without the imputed data.

Logistic regression models will be used to compare the demographic characteristics of participants who provided 18 months of EHR data as compared with participants who were lost to follow-up within the EHR or withdrew consent for study participation to identify possible differential attrition. For primary and secondary outcomes analysis, the planned likelihood-based analysis will produce unbiased results if the data are MAR; that is, not related to the unobserved value of the outcome, but can be related to observed values of the outcome or model covariates.

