#### 8.1.5 Potential Physical Risks

*Cross-reference: UNC IRBIS Application section A.6.9, A.6.10.*

There is some potential risk that participants may experience increased pain if they reduce or discontinue their opioid medication.

We expect any side effects to be rare or infrequent and mild-to-moderate.

This study is comparing two different behavioral interventions for patients with chronic pain who are already on chronic opioid therapy. Some of the intervention content is about tapering or discontinuing opioids. The participant may choose to request to taper or discontinue opioids. Lowering the dose of opioids has the potential for side effects from withdrawal. But, there are no extra risks from this study compared to discontinuation as part of usual care.

The approach of this trial is to promote a controlled opioid reduction, which in some cases might lead to complete discontinuation, with a patient's consent. The protocol does not specify or foresee abrupt tapering.

If patients do choose to taper, the physicians will be doing a very gradual taper of their opioids (as per CDC guidelines, 10% per week), which has rare to infrequent risk of withdrawal. If withdrawal is experienced, mild to moderate symptoms are expected. These symptoms may include low energy; irritability; anxiety; agitation; insomnia; sweats; muscle aches and pain; as well as abdominal cramping, nausea, and vomiting. Patients will be advised to call their provider if they experience symptoms of withdrawal.

To reduce physiological risk, certain safeguards will be implemented at RTI and at all clinical institutions. Procedures to reduce clinical risk include intensive medical monitoring of AEs and medical management common for this study population.

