3.2 Outcomes

3.2.1 Primary Outcome

The primary outcome is **change from baseline in average daily opioid dose in MED**. The daily MED for each prescription will be calculated by multiplying the quantity of each prescription by the strength of the prescription by the MED conversion factor and dividing it by the total days supply. The primary outcome will be examined at baseline and months **3, 6, 9, 12, 15 and 18** using opioid prescription information recorded in the EHR from 90 days prior to randomization until 18 months after randomization, as provided by the PCORnet common data model (CDM) data warehouse at each site. For each timepoint, the primary outcome will be derived including all opioid medications prescribed 90-days prior to the desired timepoint. The primary timepoint is 12 months; key secondary timepoints at 6 and 18 months.

Derivation of this outcome is provided in section 9.2.

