9.2 Variable Definitions

The table below provides a description of the study endpoints and subgroup categories, including data type and derivation. More information regarding these variables is provided in the analysis dataset specification file.

Variable	Type	Definition
Primary Outcome		
Change in opioid dose (based on average daily MED) from baseline to 12 months post-randomization	Continuous	
The primary outcome will be derived from EHR data from the Mid-South CDRN data warehouse. Total morphine equivalents for each prescription will be calculated by multiplying the quantity of each prescription by the strength of the prescription (milligrams of opioid per unit dispensed). The quantity-strength product is then multiplied by conversion factors to estimate the milligrams of morphine equivalent to the opioids dispensed in the prescription. The total average dose in morphine equivalents per day supplied is calculated by summing the morphine equivalents for each prescription filled during a given period and dividing by the number of days supplied. The below algorithms further describe derivation of the primary outcome measure:
 $\text{One Prescription's MED Daily (MEDD)} = \frac{(\text{Strength per unit}) \times (\text{Quantity dispensed}) \times (\text{MME Conversion factor})}{(\text{Days Supply})}$ $\text{Avg. MEDD per Timeframe} = \frac{(\text{Multiply each RX's MEDD by Days Supply}) \text{ then } (\text{Sum all RX's Total MEDD for those prescriptions within timeframe})}{\text{Total number of days in timeframe}}$ 
Opioid dose will be calculated as the prescribed milligrams of daily MED averaged over the 90 days prior to randomization and averaged over 90-days for the time periods of 3, 6-, 9-, 12-, 15- and 18-months post randomization.
 
We expect no missing prescriptions, yet some participants might not have complete data because (a) they discontinued and removed consent to use data after that date, (b) they were lost to follow-up and may have moved out of the clinic's care, (c) the last CDM transfer did not contain their data up to 18 months past baseline or (d) they discontinued taking opioids. Cases of (d) will be identified by the response to the T2 and T3 survey item G20 "Are you currently taking an opioid medicine now?". If the response indicates "no" and opioid prescriptions last dose date ends before month 18, then an MED of zero will be assumed for all days after the last dose date to Month 18 (or date participant removed informed consent, if applicable). Otherwise, if there is not a "no" response

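### The displayed MED formula in SAP 9.2 gives full credit to an order that is stopped early and replaced, and the prose beside it uses a different denominator

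*SAP*

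**What the plan says.** The primary outcome comes from prescriber orders in the EHR. SAP 3.2.1 states that "the primary outcome will be derived including all opioid medications prescribed 90-days prior to the desired timepoint".

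SAP 9.2 gives the derivation twice in one table row:

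- The displayed algorithm computes a daily MED per prescription, then says "Multiply each RX's MEDD by Days Supply", sums these totals over the window and divides by "Total number of days in timeframe".
- The prose describes "summing the morphine equivalents for each prescription filled during a given period" and then "dividing by the number of days supplied".

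On the available fields, Protocol 4.1.1 describes "Prescribing data (including drug name, start and stop dates, dose, and frequency" among others. Protocol 5.3.3 (Missing Data) says "MED will be derived using only the standardized and highly accurate fields: drug name, strength, and number of pills".

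No section shortens an order at its stop date, removes an order that another has replaced, or deals with overlapping supply. The nearest rules do not reach the case:

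- SAP 4.4.3 checks for duplicate records. A replacement at a different strength is not a duplicate.
- SAP 7.3 covers partly missing prescription fields and refers to SAP 9.2 for all assumptions.
- The last-dose rule in SAP 9.2 concerns only the time after a participant's final prescription.

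SAP 9.2 also refers to an analysis dataset specification file, which is not among the documents.

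**The concern.** Multiplying a daily MED by its own days supply cancels the days supply. What remains is strength × quantity × conversion factor, the whole order. If an order is stopped partway through and a lower-dose order starts, the displayed algorithm counts the unused remainder of the first order on top of the second. Mid-supply replacement is one way a dose change can be written, so the miscount can fall on the event the trial measures.

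The 12-month change drives the primary test. The same window averages feed the indicator for a change of at least 10 MED (SAP 9.2 and 9.4) and the table of participants with more pain and less opioid (SAP 9.6.6). In those two displays an error of several MED in one participant can move that participant across a category boundary.

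**Working it through.** **Inputs.** Window of 90 days (SAP 9.2). Typical prescription length of 30 days (Protocol 5.2.3). Mean baseline dose of 55 MED (Protocol 5.4). Design difference of 10 MED with SD 40 and 80% power (SAP 6). Assumptions not in the documents: the day of replacement, a replacement dose of 45 MED, and a replaced order that starts on the first day of the window.

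**Plan's own figure.** A two-sided 0.05 test of 10 MED with SD 40 needs 252 per arm by the normal formula. With 253 per arm, power from the noncentral t distribution is 80.1%. The stated 253 is reproduced and is not in dispute; it only sets the scale.

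**Step 1: overstatement from one replaced order.** A 30-day order at dose D that is replaced after k days is credited for 30 days but in force for k. The excess in the 90-day average is D × (30 − k)/90.

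- k = 10: 55 × 20/90 = 12.2 MED
- k = 15: 55 × 15/90 = 9.2 MED
- k = 20: 55 × 10/90 = 6.1 MED

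**Step 2: effect on a cut from 55 to 45.** To isolate the overlap, only supply days inside the window are counted here. In-force average: [55k + 45(90 − k)]/90. With the first order credited in full: [55 × 30 + 45(90 − k)]/90.

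| Replaced on day | In force (change from 55) | First order in full (change from 55) |
|---|---|---|
| 10 | 46.1 (−8.9) | 58.3 (+3.3) |
| 15 | 46.7 (−8.3) | 55.8 (+0.8) |
| 20 | 47.2 (−7.8) | 53.3 (−1.7) |

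Read literally, the algorithm also credits in full the last replacement order, which runs past day 90. It then gives (55 × 30 + 3 × 45 × 30)/90 = 63.3, a change of +8.3, for all three days.

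**Step 3: largest cut that is hidden.** Setting 30D + (90 − k)r = 90D gives a replacement dose r = 60D/(90 − k). Any cut up to 1 − 60/(90 − k) shows as no change or an increase: 25% for day 10, 20% for day 15 and 14% for day 20.

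**Step 4: the other denominator.** If the prose governs and supply days are summed, the same four orders give (55 × 30 + 3 × 45 × 30)/120 = 47.5, a change of −7.5. The in-force changes are −8.9, −8.3 and −7.8, so the cut is attenuated. The result is a weighted mean of 45 and 55 and cannot exceed 55.

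**Step 5: baseline window.** The same overlap before randomization adds the same 12.2, 9.2 or 6.1 MED to that participant's baseline, and the later reduction looks larger by that amount.

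**Step 6: from participant to arm.** If a share p of an arm has one day-15 replacement in the 12-month window, that arm's mean rises by 9.2p, and the contrast moves by 9.2 × (p₁ − p₂). An assumed imbalance of 10 percentage points gives 9.2 × 0.10 = 0.9 MED. Equal shares at equal doses cancel.

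**The case against.** The strongest reply has five parts.

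1. **The prose denominator.** If days supplied governs, no cut can turn into an increase. This is correct, but the prose conflicts with the algorithm beside it. The algorithm is the likelier operative rule, because SAP 9.2 also describes the dose as averaged over 90 days.

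2. **Scale.** An error in one participant is not comparable with a 10-MED difference between group means. A reader might infer from the 9.2 MED figure that a single replacement rivals the trial's target effect; Step 6 shows that it does not. In addition, only overlaps in the months 9–12 or baseline windows enter the 12-month change directly. Protocol 6 says the first three months are the most intensive in both arms.

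3. **Arm difference.** A reader might infer differential bias from Protocol 6.2.1, which says Arm 1 patients who change dose may be seen more often. The same section calls this standard practice. Arm 2 also has a guideline-concordant prescriber, and therapists pass on a wish to reduce (Protocol 6.3). More visits are not the same as orders replaced mid-supply. The documents do not support an arm difference.

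4. **Extreme tapers.** Protocol 8.1.5 says "the physicians will be doing a very gradual taper of their opioids (as per CDC guidelines, 10% per week". A reader might infer weekly replaced long orders and a very large error. Nothing says how orders are written during a taper, and changes made at renewal create no overlap.

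5. **Field quality and unseen rules.** The field restriction in Protocol 5.3.3 guards against unusable dosing instructions and shows a deliberate preference for accurate fields. The documents do not say how complete stop dates are, or whether they record cancellation or planned run-out. The specification file may already contain a rule. The prose also speaks of filled prescriptions, and an unfilled order would drop out, but the documents name no source of fill data.

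These points remove any claim about the size or direction of bias in the arm contrast. They also argue against making truncation the primary definition. They do not supply the missing rule or reconcile the denominators.

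**Conclusion.** The point holds as a defect in the stated derivation. Under the displayed algorithm, a 30-day order replaced mid-supply within a window overstates that participant's average by 6.1 to 12.2 MED at 55 MED (replacement on day 20 to day 10). In the months 9–12 window a modest cut can be hidden or reversed; in the baseline window the reduction is exaggerated. Under the prose denominator, the worked cut is attenuated and cannot be reversed. The two denominators contradict each other and must be reconciled.

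The documents do not show that the primary comparison is biased. Baseline orders precede randomization, so overlap there should not differ systematically by arm. For follow-up windows, neither the frequency of early replacement nor its balance is given. The conclusion assumes 30-day orders, the plan's mean dose, and no overlap rule in the unseen specification file.

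**What to change.** Amend SAP 9.2 in two places, before outcomes are compared by arm.

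1. State one denominator, the number of days in the timeframe, and delete or correct the sentence that divides by days supplied.

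2. Add a prespecified sensitivity analysis of the primary outcome. Suggested text: *Each order contributes its daily MED only on days from its start date to the earliest of its run-out date, its recorded stop or cancel date, the start of an order that replaces it, and the end of the window. Concurrent orders for different products are summed. The number of truncated orders will be reported by arm and window.*

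If the specification file already contains an overlap rule, move it into SAP 9.2.

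The cost is SAP wording and programming on fields that Protocol 4.1.1 lists; no new data collection is needed. The downside is that stop dates may be incomplete and some tablets from stopped orders may still be taken, so both versions should be shown. If early replacement is rare, the two will agree and the primary result is easier to defend. If it is common, the counts will show where the definition matters.

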
Variable	Type	Definition
		
to this item at the applicable T2 or T3 survey, or the survey was not completed, then the data after the last dose date ends will be considered missing in the calculation of the average MED across the 3-month time intervals.
 
NOTE: Section 5.3.1 in the protocol states the time periods of 4-, 6-, 8-, 10-, 12-, 14-, 16-, and 18- would be used; however, that was an inadvertent typo and it is correctly stated in protocol section 5.2.1.
 
For each of the post-randomization periods, change in daily opioid dose will be computed as the difference between the dose calculated during that period and the dose from the baseline period.
 
Further documentation regarding the medications included in the derivation of average daily opioid dose (MED) can be found in the supplemental file titled “INSPIRE_SAP_Suppl_Opioid_Meds”

Average percentage change in MED (based on average daily MED) from baseline period	Continuous	Percent change is calculated as the change from baseline divided by the baseline value. For example, if average baseline is 30 and average post baseline is 20, percent change is $(20-30)/30 =$ decrease of 33%. Alternatively, if average baseline is 30 and average post baseline is 40, average percent change is $(40-30)/30 =$ increase of 33%.
Average relative amount of MED from baseline (based on average daily MED)	Continuous	
If warranted based on evaluation of the data prior to database lock, we may evaluate average relative change rather than actual change – defined as the value in the post baseline timepoint divided by the baseline value.
 
For example, if average baseline is 30 and average post baseline is 20, average relative change is $20/30 = 2/3$rds of the average baseline MED.
 
If determined not warranted, this variable will not be calculated.

Indicator for change from BL of at least 10 MED	dichotomous	Calculated at 3, 6, 9, 12, 15, 18
Secondary Outcomes		

Variable	Type	Definition

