Change in Brief Pain Inventory (BPI) pain severity summary measure from baseline to 6- and 12-months post-randomization.	Continuous	
The BPI assess pain at its “worst”, “least”, “average”, and “now”. Although clinical trials often use pain at “worst” and “average” to represent single pain severity, the BPI’s developers recommend that all four severity items be used, because the models for validation of the BPI included all four items.
 
A composite pain severity score is derived by taking a mean severity score of the four severity questions, if all four items are answered.
 
The BPI severity score is also used to define the participant’s baseline pain severity.
 
The BPI User Guide is found at: https://www.mdanderson.org/documents/Departments-and-Divisions/Symptom-Research/BPI_UserGuide.pdf

BPI pain severity categories	Categorical	
BPI pain severity sub score categories at baseline are defined as (Boonstra 2014):
 
Mild: < 3.5
 
Moderate: 3.5 – 7.4
 
Severe: 7.5+

Change in Brief Pain Inventory (BPI) pain interference summary measure from baseline to 6- and 12-months post-randomization.	Continuous	
The BPI measures how much pain has interfered with seven daily activities: general activity, walking, work, mood, enjoyment of life, relation with others, and sleep. BPI pain interference is scored as the mean of the seven pain interference items, This mean can be derived if more than 50% (or 4 of 7) of the total items have been completed.
 
The BPI User Guide is found at: https://www.mdanderson.org/documents/Departments-and-Divisions/Symptom-Research/BPI_UserGuide.pdf

Variable	Type	Definition
Discontinuation of opioid medications (from T3 Survey) self-report	Binary	
Discontinuation of opioid medication at 12-months will be defined as a response of "No" to the G20 question on the T3 survey that asks: "Are you currently taking an opioid medicine now? Commonly prescribed opioids include hydrocodone, oxycodone, codeine, morphine, and fentanyl." If a participant responds "No" to the survey but has opioid prescriptions in the EHR within 15-days prior to the 12-month timepoint throughout the 18-month timepoint, the participant will be considered as still taking opioid prescriptions.
 
A response of "don't know" will be lumped with a response of yes, both indicate the patient has not discontinued their opioid.

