9.6.3 Discontinuation of Opioid Medications at 12-Months

Opioid discontinuation is an exploratory outcome. Opioid discontinuation at 12 months is identified on the T3 survey with supporting evidence from the prescription record (see definition above in chart). Note the protocol describes an analysis of time to opioid discontinuation, yet this was modified during the analysis planning stage prior to database lock as based on the T3 survey due to complications of not being able to identify absent prescriptions in the electronic record as being due to opioid discontinuation or a participant switching medical care outside the site's health care system.

Contingency table methods will be used to generate point and interval estimates by intervention arm. Treatment groups will be compared using an unadjusted chi-squared test. Event rates are expected to be too small to stratify by clinical site. If event rates are large enough for the risk difference to be relevant, the risk difference 95% CIs will be based on Wald-type CIs under the null hypothesis as specified by Sato. If the expected cell counts < 5, groups will be compared with a Fisher's exact test, and the exact risk difference 95% CI will be obtained using the score statistic based on Chan and Zhang (ref Chan, Zhang 1995). Where specified, Binomial 95% CIs for proportions are based on the exact Clopper-Pearson method (ref Clopper, Pearson).

In SAS, using PROC FREQ:

The chi-square test and corresponding risk difference 95% CI are obtained by:

```
table Intervention*Opid_discont / riskdiff(method=wald equal
  var=null) chisq ;
```

For small expected cell counts, the exact test and risk difference 95% CI are obtained by:

```
table Intervention* Opid_discont / fisher; exact riskdiff
  (method=score);
```

9.6.4 Pre-Specified Subgroup Tests of Heterogeneity and Interaction with Intervention Type on Opioid Use

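### Read literally, the zero-MED rule in SAP 9.2 continues past a T3 'Yes' or 'don't know' and past death, so it can put unsupported zeros in the 12-month primary window

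*SAP*

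**What the plan says.** The primary-outcome row of SAP 9.2 lists four reasons for incomplete prescription data: (a) consent removed, (b) lost to follow-up, (c) the last data transfer falling short of month 18, and (d) opioids stopped. Death is not among them. For the last reason, "Cases of (d) will be identified by the response to the T2 and T3 survey item G20", which asks whether the participant is taking an opioid now. A 'No', together with a last dose date before month 18, triggers the rule: "then an MED of zero will be assumed for all days after the last dose date to Month 18". One early end is given in brackets: "or date participant removed informed consent, if applicable".

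The alternative branch makes the days after the last dose date missing when there is no 'No' "to this item at the applicable T2 or T3 survey, or the survey was not completed". The SAP does not define which survey is applicable to which days. It has no sentence for a participant who answers 'No' at T2 and something else at T3.

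The discontinuation row of the same table uses T3 only. There, 'Yes' and 'don't know' both mean not discontinued. A T3 'No' is overruled when the participant "has opioid prescriptions in the EHR within 15-days prior to the 12-month timepoint throughout the 18-month timepoint"; then "the participant will be considered as still taking opioid prescriptions".

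SAP 9.3 defines the 12-month value, on which the formal test rests, as the average from month 9 to month 12.

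**The concern.** G20 describes the day on which it is answered. A 'No' at month 6 is evidence about month 6 and, with no prescriptions, reasonable evidence for some time after. It is not evidence about months 9 to 12 once the participant has said at month 12 that opioids are being taken. Yet the rule carries the month-6 answer to month 18 and does not say that a later answer displaces it.

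SAP 9.6.3 explains why the discontinuation outcome was moved to the survey: an absent prescription may mean stopping, or "a participant switching medical care outside the site's health care system". A T2 'No', no further prescriptions at the site and a T3 'Yes' is the pattern such a participant could produce. The literal rule scores that person as a complete responder at the primary timepoint.

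Death raises a separate problem. It is a monitored safety outcome (SAP 9.7), yet under the written rule the months after it receive the lowest possible dose.

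These zeros count as observed data. They enter the percent-change analysis as -100% and the 10 MED responder analysis as successes. They also lower the percentage missing at month 12, and SAP 9.4 starts its missing-data analyses only when that percentage exceeds 20%. The tipping-point analysis additionally needs a significant result, and it varies only values that are missing.

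**Working it through.** **Scale.** The plan gives no figure for this rule. The planning figures borrowed for scale do reproduce. A difference of 10 MED, SD 40, two-sided 0.05 and 80% power (SAP 6) give 253 per arm with the noncentral t (252 with the normal approximation), so 506 in total; 506 × 1.2 = 607.2, in line with the stated 608.

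**Applying the rule day by day.** Assumptions: 30-day months, 90-day windows, 55 MED/day while prescribed (the planning mean in Protocol 5.4), T2 at day 180 and T3 at day 360. Entries are average MED in the window ending at each month.

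| History | 3 | 6 | 9 | 12 | 15 | 18 |
|---|---|---|---|---|---|---|
| A. Last dose day 150, T2 'No', T3 'Yes'; literal rule | 55 | 36.7 | 0 | 0 | 0 | 0 |
| A, if the T3 answer alone governs all days after the last dose | 55 | 55 | missing | missing | missing | missing |
| B. Last dose day 150, T2 'No', death day 200; literal rule | 55 | 36.7 | 0 | 0 | 0 | 0 |
| C. As A, plus a prescription on days 241-300; literal rule | 55 | 36.7 | 18.3 | 18.3 | 0 | 0 |
| D. T3 'No', last prescription ends day 390; literal rule | 55 | 55 | 55 | 55 | 18.3 | 0 |

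The part-filled windows are 60 × 55 / 90 = 36.7 and 30 × 55 / 90 = 18.3. In the second row month 6 is 55 because only the 60 days with known dose are averaged.

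- History A yields two different primary values from one SAP: a change of 0 - 55 = -55 at month 12, or a missing value. On the first reading the participant has zero MED in the primary outcome and is not discontinued in the T3 endpoint.
- History B is scored zero at months 12, 15 and 18, all after death. In the month-9 window (days 181-270), only days 181-200 were lived.
- History C shows that a later recorded prescription is counted. It moves the last dose date, and zeros start only after it.
- History D leaves month 12 at the full prescribed dose.

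**Size.** 526 randomized (SAP 6) gives 526/2 = 263 per arm. A participant at 55 MED scored zero instead of unchanged moves the arm mean by 55/263 = 0.21 MED. If shares p1 and p2 of the two arms are affected, the arm difference moves by 55 × (p1 - p2). The documents give neither share. An assumed excess of 1% in one arm gives 0.55 MED, 3% gives 1.65, 5% gives 2.75 and 10% gives 5.5. A shift of 10 MED would need an excess of 10/55 = 18 percentage points. For comparison, the approximate standard error of the arm difference, ignoring missing data and clustering, is 40 × √(2/263) = 3.5 MED.

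**The case against.** The best defence is the word 'applicable'. It can be read as tying each answer to its own period, so that a T3 'Yes' makes the later windows missing and history A never yields a zero at month 12. SAP 9.2 also refers to an analysis dataset specification file, which is not among the documents and may say so. This stands in part: the T2/T3 conflict is an unresolved ambiguity and not an explicit instruction. A primary-endpoint rule that two programmers could code differently still belongs in the SAP. The word does nothing for death.

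The rule also has a real safeguard. Absent prescriptions with no 'No' become missing, so people who leave the health system without reporting a stop are not zeroed.

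On death, it can be said that deaths are reported by arm in SAP 9.7 and that SAP 9.7 describes event rates as small. Both are true. Whether a zero after death is acceptable depends on the estimand, but the SAP states no such choice; the zeros follow only from the missing end date.

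Several stronger readings are tempting, and the documents do not support them:

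- *A single 'No' is enough, or a later prescription is ignored.* The last dose date must also precede month 18, and history C shows that later prescriptions count at their dose.
- *A T3 'No' with prescriptions to about month 14 makes the two endpoints contradict each other.* History D shows otherwise. Still taking at month 12 and zero after the supply ends describe different times, and only months 15 and 18 are touched.
- *The SAP treats a change of health system as the main threat.* SAP 9.6.3 gives it as a complication behind redefining an exploratory outcome, and does not rank it.

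**Conclusion.** The concern holds in two specific situations. First, when T2 is 'No' and T3 is 'Yes' or 'don't know', the literal rule puts zero in the 9-to-12-month primary window of a participant who has not reported being off opioids at month 12, and the SAP's wording does not settle whether that is intended. Second, zeros run on after death, because consent removal is the only stated early end.

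The size is unknown and probably modest. The 0.21 MED per participant is an upper figure for someone at 55 MED whose dose would otherwise be unchanged; it scales with that person's baseline. It is smaller if the value would instead be missing, because the mixed model then draws on earlier windows that are already reduced, and cases in both arms largely cancel in the comparison. An assumed one-arm excess of 3% moves the difference by 1.65 MED, about half the approximate standard error and one sixth of the 10 MED target. A reader should not infer that this alone would overturn the primary result. It should be corrected because it sits in the primary outcome, none of the planned sensitivity analyses would reveal it, and the repair is small. Sample size is unaffected.

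**What to change.** Amend the primary-outcome row of SAP 9.2 before the arms are compared, so that the choice cannot follow the result:

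1. The most recent G20 answer governs. If T3 is 'Yes' or 'don't know' after a T2 'No', days without a prescription in the windows ending at month 12 and later are missing, not zero. This replaces the undefined 'applicable'. History A then reads 55, 36.7, 0, missing, missing, missing.
2. Zeros end at the earliest of death, consent removal or month 18, and days after death are not scored as zero. History B then has no value at months 12, 15 and 18.

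State also that missing or unscored days leave the denominator. The averaging formula in the same row divides by all days in the timeframe, so days dropped only from the numerator would still act as zeros.

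The cost is a few sentences, a few lines of derivation code and slightly more missing windows among participants with conflicting answers or who die. A broader remedy, voiding a 'No' whenever a prescription is active on or after the survey date, is not advised: it would discard true zeros from participants who had stopped while their last supply was still nominally running.
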